Our long-term goals are to develop, evaluate, and implement virtual reality interventions that enhance vocational recovery from SMI. The objectives of this application are to: 1) evaluate if VR enhances SE outcomes and if the benefits of VR generalize to improved social skills and reduced psychological distress; and 2) identify facilitators and barriers associated with large-scale implementation of VR. **Our central hypothesis is that VR will enhance vocational outcomes in a SE program.** This hypothesis is based on our research showing that VR performance predicted greater odds of receiving a job offer and a shorter duration until receiving a job offer, and recommendations from a community advisory board of SE leaders and staff. We also recognize that VR needs research to maximize the effectiveness of VR in real-world settings.

In this application we propose to conduct a single-blinded confirmatory effectiveness RCT (and a process evaluation) of VR by comparing subjects receiving SE with VR (instead of clinician role-plays) (SE+VR) to subjects receiving SE as usual (SE Only). Subjects will include adults with SMI who are newly enrolled in SE at Thresholds, the largest community mental health service provider in Chicago. We are well prepared to conduct this study because our team has extensive experience with community-based vocational and implementation research, and in leading prior studies at Thresholds. The Specific Aims are:

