### **B. Study Design**

This is a two arm randomized, single blinded, intent-to-treat, controlled trial (RCT) with baseline and pre-test assessments, up to 10 hours of VR training, post-test assessment, and follow-up at 6 months and at 9 months. We will evaluate both person-level and system-level outcomes associated with implementing VR at Thresholds. At the person-level, we propose to evaluate if IPS+VR, as compared to IPS Only, is associated with better employment outcomes (higher employment rate, shorter time-to-employment), job interviewing skills, and greater reductions in psychological distress. Interviewing anxiety and self-efficacy will be explored as potential mechanisms in the pathway between IPS and employment. At the system-level, we propose to conduct a cost-effectiveness analysis and budget impact analysis between IPS+VR and IPS Only as well as explore whether Employment Specialists (Thresholds Staff that work one-on-one with clients) working at Thresholds spending fewer hours leading interview training is related to spending more hours completing job applications with clients and building a network of employers. We will also explore if VR generalizes to social skills at both the person-level (via job retention measures) and the system-level (using a time log completed by Employment Specialists regarding time spent coaching communication skills at work).

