The Thresholds Research Coordinator will schedule the study participants to complete 6 two-hour sessions of VR. When participants show up for the VR training, the visit will be run the Thresholds research staff who will provide the trainee with an initial orientation to VR and then monitor the trainee's access and performance scores during the sessions. After completing the initial 6 visits, trainees will move on to complete their post-test visit. Trainees will be invited to use VR as-needed after completing the post-test visit, which will be monitored by the Team Leaders. Those participants assigned to the SE as usual group will have the option to use the VR training in the context of their regular use of Thresholds services (i.e., they will not have access to the study resources to use VR) following the completion of their participation in the study (after their 9-month follow-up phone call). At each training session, any subject who has had to travel to use the intervention will receive \$10 to reimburse them for the cost of transportation.

A note on VR delivery procedures (1/29/18): When the study initially began, Employment Specialists and Team Leaders were asked to run the VR orientation and training sessions. Due to workload expectations and coordination barriers, this responsibility was moved to the Thresholds Research Team.

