Alternatively, if participants are unable to attend visit 10 and/or 11 in person, the study team will schedule a series of brief phone calls in order to collect the self-reported study data by phone. In addition, the study team will offer participants the opportunity to complete their follow-up role-play assessment by means of a videoconference through BlueJeans. The BlueJeans videoconference will then be recorded by the University of Michigan research team that is approved for this study and the recordings will be stored using the previously approved methods for storing audiovisual data.

Alternatively, if the participants do not want to complete the videoconference then the participants will be offered the opportunity to complete their follow-up role-play assessment by means of a teleconference through BlueJeans. The BlueJeans teleconference will then be recorded by the University of Michigan research team that is approved for this study and the recordings will be stored using the previously approved methods for storing audiovisual data.

**D. 9. Monthly Check-in Telephone Calls for Thresholds Clients (completed via telephone) will be a repeat of procedures of the Monthly Check-in Telephone Calls for Thresholds Clients (see D. 8.).** These calls will be scheduled at monthly intervals after completion of the 6-month follow-up until the 9-month follow-up (see D. 11.), for a total of 2 calls.

D. 10. The 9-Month Follow-Up for Thresholds Clients (completed via telephone) will include only the Follow-up Employment History interview that will assess how many job interviews were completed, total hours worked, how many jobs were offered (and accepted), hourly wage, type of job, jobs terminated (and why).

The 9-Month Follow-Up Telephone Call will last approximately 10 minutes. If participants complete at least one of the two check-in calls between the 6-Month and 9-Month Follow-Up calls, they will be paid \$10 by Thresholds after the completion of the 9-Month Follow-Up call.

**D. 11. Participation Complete.** If a Thresholds client becomes employed prior to the 6-month follow-up call, they will still participate in monthly check-in phone calls and the 6-month follow-up. Their participation in the study will then be complete after completing the 6 month visit.

If the participant becomes employed between the 6- and 9-month follow-up calls, the participant will be asked additional questions on their next check-in call, which will be their last check-in.

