Data Analysis Plan for Aims 1 & 2. In this intent-to-treat study, we will collect data on 160 subjects. The biostatistician will monitor the data for distribution normality and transform abnormally distributed variables if needed. Correction for Multiple Comparisons: To minimize spurious findings, we will adjust the 3 primary tests using a false discovery rate at 0.05 (see below). Covariates: Although randomization should protect against group differences, we will covary for any between-group differences that are observed regarding demographic, cognitive, clinical and vocational history, booster sessions, and the number of completed interviews. Missing Data: We will follow the intent-to-treat principle and in longitudinal analyses we will use multiple imputation models to analyze the data in the presence of missing data. Data processing and cleaning will occur during the study, including checking for missing data and inconsistencies. All videos will be stored on the project's secure server. A Data Safety and Monitoring Board will monitor for adverse events (see 15.0 below).

**Hypothesis 1:** IPS+VR trainees will have higher employment rates than IPS Only by T3. **To test H1**, we will use multiple logistic regression and a Wald Chi-square test of the coefficient to its standard error, to compare the adjusted employment proportions in the two conditions (attained a job=1 vs. failed to attain a job or censored with a job=0, between T1 and T3). We calculated power using simulation in R, correcting for small samples and multiple testing with false discovery rate for the 4 primary tests (our power analysis is conservative, relying on Bonferroni corrections for all tests). Accounting for 10% missing, our trial that recruits 80 subjects in each arm has 80% power for a two-sided 0.05/4=.0125 level test when the OR = 3.2, with IPS+VR effectively doubling the

rate from 25% to 53% employment. Based on our earlier study where we found an OR of 8.7, or effectively tripling the employment rate from 25% to 75%, and a power of 0.99 at this magnitude of effect, we feel confident that we will have sufficient power in this study.

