**Hypothesis 2:** IPS+VR trainees will have greater improvement in *job interview skills* than IPS Only by T2. **To test H2**, we will conduct a repeated measures analysis of variance (RM-ANOVA) with pre and post interview scores as the repeated measures and treatment group as the fixed factor. Based on our pilot data, we expect r=.7 between T1 and T2 scores, and an effect size of d=.67 between pre and post interview role-play scores using VR. Assuming a small-to-moderate effect within IPS Only (e.g., d=.25), our best power estimate assumes a medium effect size contrasting IPS Only with IPS+VR (d=.67-.25=.42). This effect size and correlation imply an expected 6.9% reduction in within subject error for the treatment–x-time effect. Thus, 80 subjects at .0125 level will yield 82% power to detect this effect. For the ANOVA model, 160 subjects will be sufficient to detect a reduction of within subject error of 4.7% with 80% power. Assuming a full sample effect size of d=.46 (.67+.25)/2), this reduction in error corresponds to an effect size of d=.62 for the IPS+VR group and d=.30 in the IPS only group (a difference of d=.32).

**Hypothesis 3:** IPS+VR will get jobs sooner than IPS only by T3. **To test H3**, we will use a Cox proportional (or non-proportional) hazards regression model to assess the adjusted hazard rate on time-to-employment for IPS+VR vs. IPS Only, adjusting for potential covariates (e.g., completed training trials). For a power analysis for **H3**, we assume a constant hazard rate for the distribution of time-to-employment in both groups. We also assume that a proportion of 0.20 of the subjects in the IPS Only group will find a job by T3 (that is, a hazard rate of 0.0085 for IPS Only). This analysis is estimated based on limited pilot data and log-rank power tables. Thus, 160 subjects provide 80% power for a 0.0125-level test comparing time-to-employment in the two arms to detect a hazard rate of 2.0 for IPS+VR vs. IPS Only.

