**Hypothesis 5:** IPS+VR will be more cost-effective than IPS Only. To test **H5**, we will conduct a costeffectiveness analysis (CEA) to assess the short-term cost-effectiveness of IPS+VR relative to IPS Only using a societal perspective, which includes intervention costs and client costs provided by the IPS program director. Intervention costs include variable costs (e.g., time spent by ECRs) and fixed costs (e.g., costs supporting hiring, training, and coordination). Client costs will include time using VR and travel costs. We will use standard approaches to identifying and assigning unit costs for each cost component. We will use job attainment rate as our measure of effectiveness. The main step is to calculate an incremental cost-effectiveness ratio (ICER), which is defined as the difference in total costs between the IPS+VR and IPS Only groups, divided by the between-group difference in job attainment rate. Confidence intervals will be calculated around the ICER using bootstrapping and Fieller's theorem. We will conduct sensitivity analysis by deriving cost-effectiveness acceptability curves that display the probability of IPS+VR being cost-effective at various threshold values. **Exploratory (Person-Level):** To study the generalizability of VR to social skills, we will evaluate if more VR training (i.e., number of trials) is associated with a longer job tenure (number of weeks) and enhanced social skills using linear regression; covariates will include demographic, cognitive, vocational, and training characteristics that differentiate groups. **Exploratory (System-Level):** We will explore if, as a result of VR, ESPs reallocate their interviewing hours towards building larger employer networks, completing more job applications with clients, and engaging in more hours of coaching work communication with clients.

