**Hypothesis 6:** Improved interviewing skills will mediate the relationship between VR (number of completed VR trials and employment outcomes (obtaining employment). **To test H6**, we will test first for a significant IPS+VR impact on role-play scores compared to IPS alone, then check for treatment by mediator interaction, then on the product of the two coefficients with bootstrapped confidence intervals. We simulated power for this text, finding 80% power when the effect size for skills is small (effect size=0.2) and the odds for skills leading to a job is 1.8; thus we expect to have sufficient power. These older mediational models are informative but incomplete, and these will be followed by computing the *causally interpretable average natural indirect effect* under assumptions i – iv therein. We plan to conduct sensitivity analyses to the assumption of "no exposure induced mediation-outcome confounding". For the exploratory moderated mediation model, we plan to use Approach 1 of Vanderweele et al. to account for the combined mediated (indirect) effect of both the psychological changes in self-efficacy, anxiety, and role-play scores, as suggested in Corbiere et al..

**Exploratory:** To test the moderated mediation (mediated effect varies as a function of a baseline variable), we will first conduct a standard model of post-intervention anxiety/self-efficacy serving as a mediator of the relationship between VR and interviewing skills using the "product of coefficients method". Mediation tests will be based on whether the confidence interval for the product of coefficients includes zero. This approach addresses the known non-normality of the test statistic. To this standard mediation model we will include an interaction of baseline (pre-intervention) anxiety/self-efficacy to interact with VR training on post-intervention anxiety/self-efficacy. Similarly, we will include a baseline-by-intervention interaction on interviewing skills. The Johnson-Neyman approach will assess where mediation occurs as a function of baseline levels. We will test if employment outcomes mediate the relationship between interviewing skills and psychological distress at 6-month follow-up, using the same approach outlined for **H6**.

### Data Analysis Plan for Aim 3

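### H3 names completed training trials as a covariate in the arm comparison; entered as a count, this post-randomisation dose would displace the intent-to-treat hazard ratio

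*Combined protocol and SAP*

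**What the plan says.** All analysis text is in section 14.0, Data Analysis Plan for Aims 1 & 2.

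- **H3** reads the arm effect from an adjusted Cox model, "adjusting for potential covariates (e.g., completed training trials"). This is a candidate covariate, not a fixed model term, and no coding is given. No H3 model without trials is named as primary.
- **Meaning of trials.** The person-level exploratory analysis will "evaluate if more VR training (i.e., number of trials) is associated with a longer job tenure", and H6 asks whether interview skills "mediate the relationship between VR (number of completed VR trials and employment outcomes (obtaining employment"). In both places trials are the amount of VR used.
- **Control access.** Section 4.0 D.5 lets the control arm use VR only "following the completion of their participation in the study (after their 9-month follow-up phone call"). For a client employed before the 6-month follow-up, D.11 ends participation sooner: "Their participation in the study will then be complete after completing the 6 month visit". Either way there is no VR use in IPS Only before the 6-month visit.
- **Principle.** Section 4.0 B describes a "two arm randomized, single blinded, intent-to-treat, controlled trial (RCT"), and the plan adds: "We will follow the intent-to-treat principle".
- **General covariate rule.** Variables that differ between groups will be adjusted for. The list mixes demographic, cognitive, clinical and vocational history with booster sessions and the number of completed interviews. It is not limited to baseline.

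**The concern.** A covariate in a randomised comparison should be fixed before assignment. Completed trials are a consequence of assignment, and one arm cannot have any. Conditioning on them changes the question from the effect of being offered VR to the contrast between a control and an offered client who completed zero trials. Few VR clients may resemble that client, so the coefficient is largely an extrapolation.

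H3 would be judged on that coefficient. A real benefit of assignment could be reported as no effect or as harm. A spurious benefit could also appear if the count itself depends on when a client finds work. The unadjusted comparison of the arms is sound in all these cases.

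Reading trials as interview practice in general does not help. The comparison is of "subjects receiving SE with VR (instead of clinician role-plays) (SE+VR) to subjects receiving SE as usual (SE Only"), so role-play practice is also set by arm and also follows randomisation.

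**Working it through.** **Inputs from the plan (H3 and H1 text):** 80 per arm; 20% of IPS Only employed by T3; hazard ratio 2.0; level 0.0125, taken as two-sided as in H1. T3 is read as the 6-month follow-up of Aim 1. The stated hazard of 0.0085 fits this: -ln(0.8)/26 = 0.0086 per week.

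**Assumed inputs:** trial counts in IPS+VR with mean/SD 15/5, 15/8, 10/5 and 5/3. The only anchor is D.5, which requires 10 virtual interviews before home use (one interview taken as one trial). That is a condition for home use, not a dose estimate.

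**Step 1, the plan's own figure.** Event probabilities are 0.20 and 1 - 0.8² = 0.36, so events are 16 + 28.8 = 44.8. Power by the Schoenfeld formula is Φ(√44.8/2 × ln 2 - 2.498) = Φ(-0.18) = 43%, not the stated 80%. That gap is a separate point, and nothing below depends on it.

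**Step 2, what the coefficient estimates.** With linear predictor β·arm + γ·trials and trials = 0 throughout IPS Only, the log hazard ratio for a VR client with d trials is β + γd. The reported arm effect β is the contrast at d = 0.

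**Step 3, precision, by hand.** Without trials, the variance of the log hazard ratio is about 1/16 + 1/28.8 = 0.0972, SE 0.31. With the count added and no dose response, extrapolating to zero trials adds about (mean/SD)²/28.8:

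- 15/5: 0.0972 + 9/28.8 = 0.410, SE 0.64; power Φ(0.693/0.64 - 2.498) = 8%.
- 5/3: 0.0972 + 2.78/28.8 = 0.194, SE 0.44; power Φ(0.693/0.44 - 2.498) = 18%.
- No adjustment: Φ(0.693/0.312 - 2.498) = 39%.

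**Step 4, simulation.** 4000 trials per scenario, exponential times censored at T3, Wald test at 0.0125, all four count settings. In the motivation rows, motivation adds 0.5 to the log hazard per SD.

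| Scenario | Arm only | Arm + count |
|---|---|---|
| True HR 2.0, no dose response | SE 0.31, reject 38-39% | SE 0.46-0.65, reject 9-19% |
| True HR 2.0, half of the effect through dose | reject 38-39% | HR 1.41-1.43, reject 3-5% |
| True HR 2.0, trials correlate 0.3 with motivation | HR 1.93-1.99, reject 34-36% | HR 1.29-1.49, reject 3-7% |
| Same, correlation 0.5 | as above | HR 0.94-1.28, reject 1-3% |
| Same, correlation 0.7 | as above | HR 0.68-1.05, reject 1-2% |
| No true effect, correlation 0.5 | reject 0.6-1.1% | HR 0.49-0.65, reject 2-3% |

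The half-through-dose hazard ratio follows from construction: the coefficient keeps only the part that bypasses dose, √2 = 1.41.

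**Step 5, counts that stop at employment.** D.5 also allows as-needed VR use after post-test, so a total count can depend on time to employment. With no true effect, at 15/5 and 5/3 (500 replicates):

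- Training over 4 weeks that stops when a job is found: adjusted HR 2.23 and 1.26, rejection 12.6% and 3.2%.
- The same plus 0.25 as-needed trials per week until employment or T3: HR 12.6 and 10.5, rejection 66% and 79%.

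The unadjusted test rejected in 0.2-1.6%. Here the bias favours VR.

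**Step 6, coding.** Centring trials within arm gives SE 0.32 and about 37% rejection in the no-dose-response case, so the power loss belongs to the raw count. Centring is not a full remedy: with as-needed use and a true HR of 2.0, the centred estimate is 1.62-1.76.

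**The case against.** The plan says potential and e.g., so nothing commits the team to this model. The harm needs two further choices: selecting trials, and entering them as an uncentred count. It is also true that trials are the only covariate named in the H3 text but not the only candidate, because the general covariate rule covers H3 too. The trial counts, the motivation effect and the correlations are all assumed.

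These points limit the claim without removing it. The plan names an unsuitable covariate as its one H3 example and specifies no H3 model without it. An analyst following the text could report the dose-adjusted ratio as the H3 result. Neither the sizes nor the direction of the bias can be settled from the documents, as Step 5 shows. That the coefficient stops being the effect of assignment does not depend on the assumed values.

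The extension to the general rule is weaker. Booster sessions is undefined. The number of completed interviews could be the baseline count (D.3) or the follow-up count (D.8). If these are post-randomisation measures, the same problem reaches other between-arm tests, including H1. That remains conditional, and no figure is attached to it.

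**Conclusion.** The concern holds. H3 names an on-treatment dose, zero by design in one arm, as a covariate in an intent-to-treat comparison. Entered as a count, it turns the arm hazard ratio into a contrast at zero trials. Under the plan's H3 inputs and the assumed counts, the standard error grows by a factor of about 1.5 to 2.1 (0.46/0.31 to 0.65/0.31). A true ratio of 2.0 can be reported near or below 1 if trials track motivation, and a null effect can look like a benefit if training stops at employment. The sizes are illustrative and apply to raw-count entry. The plan permits this analysis but does not require it. It should be corrected before analysis.

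**What to change.** In section 14.0:

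1. Hypothesis 3: delete completed training trials as a covariate.
2. Covariates paragraph: state that between-arm tests adjust only for variables measured before randomisation. Remove booster sessions from the list, and limit the number of completed interviews to the count taken at the baseline Employment History Interview (section 4.0 D.3).
3. Keep number of VR trials as the exposure in the person-level exploratory dose analysis and in H6.
4. Label any dose-adjusted comparison of the arms as secondary.

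The cost is wording only, with no new data. Dose-adjusted between-arm estimates lose confirmatory status.

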### 3.0 Inclusion and exclusion criteria:

# We will recruit 180 IPS clients at Thresholds diagnosed with a mental disorder with or without psychotic features into the randomized controlled trial. *Inclusion/exclusion criteria are outlined below:*

Inclusion Criteria: 1) Over 18 years old;

2a) all chronic schizophrenia spectrum disorders, including schizophrenia, schizoaffective disorder, delusional disorder, brief psychotic disorder, schizophreniform disorder, other specified schizophrenia spectrum and related disorder, and unspecified schizophrenia spectrum and related disorders;

2b) all bipolar spectrum disorders beyond bipolar type I and II to include cyclothymia, other specified bipolar and related disorder, and unspecified bipolar and related disorders;

2c) all depressive disorders, including disruptive mood dysregulation disorder, major depressive disorder, persistent depressive disorder, other specified depressive disorder, and unspecified depressive disorder;2d) post traumatic stress disorder

3) fluency in English; 4) at least a 4th grade reading level; 5) enrolled in IPS; 6) active IPS enrollee as indicated by at least 1 contacts with his/her Employment Specialist in the past 30 days; 7) currently unemployed or underemployed; 8) Planning to go on interviews within 4 weeks of enrolling in the study; 9) willing to be video recorded; and 10) willing and able to provide informed consent. We will review each participant's medical record to confirm his/her mental health history.

Exclusion Criteria: 1) documented developmental or learning disability; 2) medical condition that may compromise cognition (e.g., Parkinson's Disease, Alzheimer's Disease, Huntington's Chorea, Moderate or Greater TBI); 3) uncorrected vision or hearing problems; 4) active suicidal ideation within the last 30 days with at least some intent to act, with or without a specific plan; this would be reflected in a score of 4 or 5 on the Suicidal Ideation section of the Columbia Suicide Severity Rating Scale (CSSRS); and 5) a past suicide attempt within the past 30 days that did not include preparatory acts or behavior, but was defined by a potentially self-injurious act committed with at least some wish to die as a result of the act.

We will not include any special populations: adults unable to consent; minors; infants; childrens; teenagers (ages 17 and younger); or prisoners.

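### Hypothesis 3 (time to employment): the stated 80% power at a hazard ratio of 2.0 is about 40-43% on the plan's own inputs

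*Combined protocol and SAP*

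**What the plan says.** The power statement for Hypothesis 3 is in section 14.0, under the data analysis plan for Aims 1 and 2. Its conclusion is "Thus, 160 subjects provide 80% power for a 0.0125-level test comparing time-to-employment in the two arms to detect a hazard rate of 2.0" for IPS+VR against IPS Only. Its inputs are:

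- **Hazards:** "we assume a constant hazard rate for the distribution of time-to-employment in both groups".
- **Control rate:** "a proportion of 0.20 of the subjects in the IPS Only group will find a job by T3", which the plan equates to a hazard of 0.0085 with no time unit.
- **Method:** "This analysis is estimated based on limited pilot data and log-rank power tables".

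The Hypothesis 3 sentence gives neither the split between arms nor the sidedness. The Hypothesis 1 paragraph gives both: the trial "recruits 80 subjects in each arm has 80% power for a two-sided 0.05/4=.0125 level test". No event count is given for Hypothesis 3.

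**The concern.** The power of a log-rank or Cox comparison depends on the number of events, not the number of subjects. With only 20% of controls expected to find a job by T3, 160 subjects yield few events, and the test is planned at a strict level. 80% power at a hazard ratio of 2.0 looked too high for that combination.

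Hypothesis 3 is one of the tests planned at 0.05/4. The sentence tells readers that a true doubling of the hazard would be detected four times in five. If the real figure is nearer two in five, a null result says much less about a doubling than the plan leads readers to believe.

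**Working it through.** **Inputs.** All come from section 14.0.

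- 160 subjects, 80 per arm; two-sided level 0.0125 (the last two from Hypothesis 1).
- Constant hazards; 20% of IPS Only employed by T3.
- The 2.0 is read as a hazard ratio. It is written as a hazard rate, but beside a control hazard of 0.0085 only a ratio makes sense.

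**Consistency of the inputs.** As a weekly rate over 26 weeks, 0.0085 gives 1 - exp(-0.0085 × 26) = 0.198, which matches 20%. The missing unit is therefore not the source of the problem, and the calculation below needs only the 20% and the ratio.

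**Expected events.**

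- IPS+VR employed by T3: 1 - 0.80² = 0.36.
- Events: 80 × 0.20 + 80 × 0.36 = 16 + 28.8 = 44.8, or 28% of 160.

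**Power at hazard ratio 2.0.** The critical value is 2.498, and Φ is the standard normal distribution function.

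- Schoenfeld: Φ(√(44.8/4) × ln 2 - 2.498) = Φ(2.320 - 2.498) = 42.9%.
- Freedman, the form behind the log-rank tables the plan cites: Φ(√44.8 × (2 - 1)/(2 + 1) - 2.498) = Φ(2.231 - 2.498) = 39.5%.
- Simulated log-rank test: 41.3% (40,000 trials); a separate run of 20,000 gave 40.7%.

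The stated 80% is not reproduced.

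**What 80% would need** (z for 80% power = 0.842).

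- Events, Schoenfeld: 4 × (2.498 + 0.842)² / (ln 2)² = 92.8, so 93.
- Events, Freedman: 9 × (2.498 + 0.842)² = 100.4, so 101.
- As a share of 160 subjects: 93/160 = 58% and 101/160 = 63%, against the 28% implied.
- Subjects: 93/0.28 = 332 and 101/0.28 = 361. Simulation with 346 gave 80.2%.
- Keeping 160 subjects: a hazard ratio of 2.55 (Schoenfeld, 43% employed in IPS+VR, 50.7 events) or 2.71 (Freedman, 45%, 52.3 events). Simulation gave 79.6% at 2.60.

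**Other readings**, all at hazard ratio 2.0:

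| Reading | Freedman | Schoenfeld |
|---|---|---|
| 160 subjects, one-sided 0.0125 | 49.6% | 53.1% |
| 160 subjects, two-sided 0.05/3 | 43.5% | 47.0% |
| 160 subjects, two-sided 0.05 | 60.7% | 64.0% |
| 160 subjects, one-sided 0.05 | 72.1% | 75.0% |
| 180 subjects, two-sided 0.0125 | 44.8% | 48.5% |
| 180 subjects, one-sided 0.05 | 76.5% | 79.3% |
| 25% control rate (as in Hypothesis 1), 160 subjects, two-sided 0.0125 | 49.0% | 52.9% |
| 10% missing (144 subjects), two-sided 0.0125 | 35.2% | 38.3% |
| 160 per arm, two-sided 0.0125 | 74.5% | 78.3% |

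The 0.05/3 row is there because the plan also speaks of three primary tests. The 180 comes from section 3.0 ("We will recruit 180 IPS clients at Thresholds"). The 10% missing is stated for Hypothesis 1 only.

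**The case against.** The arithmetic is not in dispute. Four arguments bear on how it should be read.

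1. **The false discovery rate.** The plan will adjust by false discovery rate at 0.05 and calls its Bonferroni-based power conservative. The level that Hypothesis 3 must meet could then lie anywhere between 0.0125 and 0.05, depending on the other p-values. This stands: operating power at a ratio of 2.0 lies between 40-43% and 61-64%. Both ends are well below 80%, and the sentence itself claims power at 0.0125.

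2. **The larger effect under Hypothesis 1.** That paragraph assumes employment rises in "rate from 25% to 53% employment". Under constant hazards this is a ratio of ln(0.47)/ln(0.75) = 2.62, with 80 × (0.25 + 0.53) = 62.4 events. Hypothesis 3 would then have about 85% (Freedman) to 91% (Schoenfeld) power. This also stands: the test is adequately powered at the Hypothesis 1 design effect. It does not support the claim made for 2.0.

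3. **The wrong number may be elsewhere.** Reading 160 as per arm gives 74.5-78.3%, so a confusion of per-arm and total numbers is possible. Alternatively, at a ratio of 2.0 a control rate of about 46-50% would give 80%. The documents do not settle the cause. They do fix 80 per arm and 20%, so the sentence is wrong as it stands.

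4. **Longer follow-up or covariate adjustment.** Extending the constant hazard to 9 months gives 55-59% at two-sided 0.0125, and the hypothesis is stated by T3, the 6-month follow-up. The Cox model adjusts for covariates, but the plan quantifies no gain and rests its power on log-rank tables.

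**Conclusion.** The concern holds. On the plan's own inputs the power for Hypothesis 3 is about 40-43%, roughly half the stated 80%, because the design yields about 45 events where 93 to 101 are needed. No reading examined with 160 subjects in total, a 20% control rate by T3 and a ratio of 2.0 reaches 80%, even with the multiplicity correction dropped and a one-sided test.

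The result rests on equal allocation, constant hazards, a two-sided test and no loss to follow-up; loss would lower it further. The error lies in the power claim and in how a null result would be read. It does not affect the validity of the planned test.

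**What to change.** First check whether 160 in total, 20% and 2.0 are the intended inputs. If they are, replace the sentence with wording such as:

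> With 160 subjects (80 per arm) and 20% of IPS Only employed by T3, power for a hazard ratio of 2.0 is about 40-43% at two-sided 0.0125 (about 61-64% at two-sided 0.05). Power of 80% at two-sided 0.0125 is reached at a hazard ratio of about 2.55-2.7. These figures are before any loss to follow-up.

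If an input was misstated, correct it and recompute, giving the expected number of events. Write hazard ratio in place of hazard rate for the 2.0.

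Optionally, note that Hypothesis 1 assumes 25% in the control arm for the same event and window. In that case give both results: 49-53% at a ratio of 2.0, and about 85-91% at the ratio of 2.62 implied by 25% against 53%.

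The cost is one rewritten sentence and a less favourable figure. Enrolment and the Hypothesis 3 analysis do not change.
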